## 2.0 OBJECTIVES

We propose a 3-group, single-blind, parallel design randomized controlled trial in prostate cancer survivors treated with ADT to compare: 1) tai ji quan to 2) strength training and each to 3) a placebo (stretching) control group.

Our specific aims and hypotheses are:

**Primary aim:** To determine and compare the efficacy of tai ji quan training and strength training in reducing the incidence of falls in prostate cancer survivors on ADT.

*Hypothesis:* Tai ji quan and strength training groups will each reduce the incidence of falls compared to a control group. The relative efficacy of each type of training to reduce falls is not yet known.

**Secondary aim:** To determine and compare the efficacy of tai ji quan training and strength training to reduce frailty and dysfunction in prostate cancer survivors on ADT.

*Hypothesis:* Tai ji quan and strength training groups will each reduce the prevalence of frailty and improve physical function compared to a control group. The relative efficacy of each type of training to reduce frailty and improve physical function is not yet known.

**Tertiary aim:** To determine how well the benefits of Tai ji quan and strength interventions persist over a 6-month period.

*Hypothesis:* Group differences in the primary outcome of falls, and secondary outcomes of frailty and physical function will remain for 6 months after the end of the supervised interventions.

**Exploratory Aim:** To explore the patterns and predictors of types of men (including host and treatment factors) who benefit most from tai ji quan and strength training.

**Ancillary study:** We have received supplemental funding to conduct an ancillary study with the following aim: Determine the relationship between mobility characteristics (gait, turning as dynamic balance) during passive monitoring of up to 7 days and ADT exposure, frailty, falls and functioning in up to 130 prostate cancer survivors.

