Interested participants will be screened either by phone or in person using an IRB approved screening script. After initial screening, potentially eligible men will be scheduled for consent and baseline screening and possible further baseline testing in qualified men. Screening includes review of fall history in the past year, a 3-meter Timed Up and Go walk at usual pace, and standing up and down from a chair five times as fast as safely possible. The testing session will include DXA, performance testing and survey completion and will be repeated at 3- and 6-mos. (post-intervention), and 6 mos. after completion of the intervention (follow-up). Total time for performance testing and survey completion is ~2-2.5 hours. Men will complete written surveys on a computer at baseline and online for follow-up visits, unless they prefer to complete paper surveys. Staff will review surveys for completeness and follow up with participants in person or by phone on missing data. To reduce bias we will retain blinding of the research assistants who conduct the testing visits, by having the Project Director provide each participant with an envelope that contains his random group assignment *after* baseline testing is complete. Qualified men will

be randomly assigned to 1 of 3 groups: 1) tai ji quan, 2) strength training or 3) stretching control. To avoid confounding and differential tolerance to exercise by ADT history and age, block randomization stratifying for timing of ADT (past or current) and will be done using EXCEL to generate random assignments from each block. Assignment will be in random blocks of 6 to 9 within each wave (~42-48 men) to facilitate even enrollment and to prevent the Project Director from predicting group assignment.

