Exploratory Aim: Determine patterns and predictors of types of men who benefit the most. We will use a growth mixture modeling (GMM) approach using Mplus to explore there are distinct types of men (based on age, baseline frailty, cancer stage, ADT duration and timing, other treatments, etc.) who benefit most from the intervention(s). GMM is a type of clustering technique that can simultaneously handle longitudinal data and multiple measures to identify distinct subgroups of patients who have different responses to an intervention. For longitudinal outcomes (e.g., Aim 2), we will employ GMM to identify distinct patterns of change in subpopulations with varying response (growth) trajectories and unique variances reflecting homogenous within-trajectory growth. Patients will be assigned to the “most likely class” or pattern of change over time (e.g., men who improve most from an intervention) and follow-up analyses (e.g., multinomial regression) will be conducted to describe the demographic and clinical characteristics of patients who are classified into different subgroups.

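### The Exploratory Aim asks which men benefit most, but its trajectory classes cannot separate treatment benefit from prognosis

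*Combined protocol and SAP*

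**What the plan says.** Section 2.0 sets the question this way: "To explore the patterns and predictors of types of men (including host and treatment factors) who benefit most from tai ji quan and strength training".

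Section 13.0, Exploratory Aim, gives the method. It introduces GMM as a clustering technique able to "identify distinct subgroups of patients who have different responses to an intervention". For the longitudinal outcomes, "we will employ GMM to identify distinct patterns of change in subpopulations with varying response (growth) trajectories". Then "Patients will be assigned to the “most likely class” or pattern of change over time". The same sentence goes on to an example class and the next step: "pattern of change over time (e.g., men who improve most from an intervention) and follow-up analyses (e.g., multinomial regression) will be conducted". The follow-up regression serves "to describe the demographic and clinical characteristics of patients who are classified into different subgroups". The characteristics named are age, baseline frailty, cancer stage, ADT duration and timing, and other treatments.

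The paragraph does not say whether control men enter the model, whether arm acts on the growth factors, or whether classes or factor levels are compared between arms. It gives no rule for the number of classes, no entropy check and no allowance for classification error.

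**The concern.** Benefit is a contrast: a man's outcome with the exercise against his outcome without it. A man in an improving class may have improved anyway, and a man in a flat class may have been kept from declining. Regressing class on baseline characteristics therefore finds predictors of trajectory. These are predictors of benefit only if natural course is unrelated to the characteristic.

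The likely product is a profile of the men said to benefit most from each programme, which could later guide who is offered which exercise. The trial already has what the right contrast needs, a randomised stretching control, but the paragraph does not use it.

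**Working it through.** **1. Does another part of the plan supply the contrast?**
- Section 13.0, covariates: age, ADT timing, fall history and baseline frailty are possible covariates. No interaction with arm is given.
- Aim 2: group by time only, with no baseline factor in the interaction.
- Aim 3: product terms with treatment, but for exercise taken during follow-up, which is post-randomisation.
- Additional Analyses: the moderators there predict continued exercise, not treatment benefit.
- Section 3.0, Additional Measures of Interest: symptoms are to be examined as moderators or mediators, with no model.

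None gives an arm-by-baseline-factor term. The plan states no figure for this aim, so there is none to reproduce. Everything below rests on assumed effect sizes.

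**2. A factor that modifies nothing.** Let change have SD 1. The factor shifts it by 0.4 and exercise shifts it by 0.4 at both factor levels, so the arm-by-factor effect is 0.40 − 0.40 = 0. Call a change above 1.2 an improvement.
- Control: P = 1 − Φ(1.2) = 0.115 without the factor and 1 − Φ(0.8) = 0.212 with it. OR = (0.212/0.788)/(0.115/0.885) = 2.1.
- Exercise: P = 0.212 and 1 − Φ(0.4) = 0.345. OR = (0.345/0.655)/(0.212/0.788) = 2.0.

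For cut-offs from 0 to 1.4 the OR is 1.90 to 2.15 in control and 1.90 to 2.00 in exercise. The factor roughly doubles the odds of improving in every arm, yet says nothing about benefit.

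**3. The planned procedure, simulated.** From the plan: 300 men, 100 per arm, at 0, 3 and 6 months. Assumed: baseline SD 1, random-slope SD 0.3, residual SD 0.5, benefit 0.4 per three-month period for every exerciser, and a binary factor with log-odds ratio 2.0 (OR about 7.4) for the better natural-course class. A two-class mixture without an arm term was fitted, men were assigned to their likeliest class, and class was regressed on the factor. There were 300 runs per row.

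| Slope gap between classes | Entropy | Misclassified | Factor flagged by class regression | Arm-by-factor test significant | Control men in improver class | Median log-OR (true 2.0) |
|---|---|---|---|---|---|---|
| 1.0 | 0.57 | 19% | 97% | 5% | 36% | 1.26 |
| 1.5 | 0.79 | 7% | 100% | 8% | 43% | 1.69 |
| 2.0 | 0.93 | 2% | 100% | 6% | 48% | 1.93 |

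Fitting only the exercise arms (gap 1.5) still flagged the factor in 100% of runs.

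The reverse case was built so that natural course hides benefit. Men with the factor gain 0.8 per period from exercise and others gain 0, but the factor worsens natural course by 0.53 per period, about two thirds of 0.8, to match the two thirds of men who exercise. The class regression flagged this true modifier in 5% of runs and the arm-by-factor test in 95%.

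**4. Assignment to the likeliest class.** If a share a of men is classified correctly, with errors symmetric and unrelated to the factor, a true class probability p is seen as p* = a·p + (1 − a)(1 − p). Take p = 1/2 against 1/3, a true OR of 2.0. The value 1/2 stays at 1/2, so the observed OR is (1 − p*)/p* with p* computed from 1/3.
- a = 0.7: p* = 0.433, OR = 0.567/0.433 = 1.31.
- a = 0.8: p* = 0.400, OR = 0.600/0.400 = 1.50.
- a = 0.9: p* = 0.367, OR = 0.633/0.367 = 1.73.

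**The case against.** The paragraph is silent on arm; it does not exclude it. The multinomial regression is only an example, and its stated purpose is descriptive. A GMM with arm acting on the growth factors within class could estimate class-specific effects, and an analyst might fit one. Section 13.0 also justifies fall history as a covariate by an interest in efficacy among men with and without recent falls, so effect modification is not wholly ignored. All of this is fair, but none of it specifies an arm-by-factor contrast, and the example class is labelled by improvement from the intervention.

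The inputs are also favourable to the concern. A prognostic OR of 7.4 is strong, so the 97% to 100% rates show direction and not likely size. An accuracy of 70% is below any simulated row (81%, 93%, 98%), and at entropy 0.93 there was almost no attenuation.

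Interaction tests are weak too. If a main effect has 80% power, effect/SE = 1.960 + 0.842 = 2.802. An equal-sized interaction over a 50:50 factor has twice the SE, so its power is Φ(1.401 − 1.960) ≈ 29%, before multiplicity. That limits precision but does not make the class regression a substitute.

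A reader might infer that assigning men to their likeliest class also makes standard errors too small. Nothing here supports that. In the set-up of step 4 with 150 men per level, the empirical SD and mean model SE of the log-OR were 0.233 and 0.233, 0.235 and 0.234, and 0.238 and 0.236 at the three accuracies. That check leaves out the uncertainty from estimating the classes, so the question stays open.

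**Conclusion.** The point holds as a mismatch between the aim and its method. As written, the analysis cannot separate predictors of benefit from prognostic factors: it can flag factors that modify nothing and miss ones that do. A reader might go further and infer that the classes show prognosis instead of benefit, or that the plan has decided against comparing arms. The documents support neither. Trajectories contain both components, and arm's role is simply not stated.

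Attenuation from class assignment is conditional: material with poorly separated classes, small at high entropy. All sizes rest on assumed effects and show mechanism and direction, not a forecast.

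Severity is minor. The aim is labelled exploratory, carries no hypothesis or power claim, and leaves the analyses of Aims 1 to 3 unchanged.

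**What to change.** Base any statement about who benefits on exploratory arm-by-baseline-factor terms for the factors the Exploratory Aim already lists: arm by factor in the falls model, and arm by time by factor in the Aim 2 models. Report estimates with confidence intervals and say that they are imprecise.

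If GMM is kept, fit it in all three arms, let arm act on the growth factors within class, and compare arm effects across classes. Relate covariates to class by a bias-adjusted three-step method in Mplus, already planned software, and report entropy. Entering arm only as a predictor of class, even with that correction, is not enough: it still yields main effects of covariates on class. Otherwise, keep the GMM as description and call the classes trajectories, not benefit.

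The cost is a few sentences in section 13.0 and modest extra analysis. The downside is wide intervals for the interactions. No new data are needed.

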### **Additional Analyses**

Injurious falls: Though the proposed study is not powered to examine reductions in injurious falls from the intervention, we will conduct an additional analysis on this important outcome. An injurious fall is one that results in fractures, head injuries, sprains, or serious joint injuries, or in a participant seeking outside medical attention. We will conduct this analysis among the subsample that had at least 1 fall using logistic regression.

Mechanisms of intervention effects on falls: We can use strength and stability measures to identify the mechanism(s) by which each exercise approach may reduce falls, strengthening support for exercise as a fall prevention strategy. We will test 3 mediators, muscle strength (chair stand time) and stability (walk speed and postural sway) as possible mediators because both measures may be affected by each intervention and each possible mediator is a major risk factor for falls. Mediation of the intervention effect by changes in performance measures will be analyzed using Mplus. A manifest model will be tested with the dummy vectors representing tai ji quan and strength training as exogenous variables, change in strength and as endogenous variables (mediators), and number of falls over the intervention period as an endogenous variable (outcome). Significant indirect parameter estimates based on standard errors using the multivariate delta method from the treatment variables to number of falls through changes in strength and stability would provide support for mediation.

Potential moderators of sustained exercise after the intervention: Linear and logistic regression models will be used to explore different predictors (e.g., age, comorbidities, timing of ADT, etc.) of adherence to exercise after structured training stops.

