## Outcome Measures

### Primary Endpoint: Falls

In this study, a fall is defined as unintentionally coming to rest on the ground or at some other lower level, not as a result of a major intrinsic event (e.g., stroke or syncope) or overwhelming hazard [13]. Falls over one year prior to baseline will be ascertained to characterize the sample and check for equality of randomization. Prospective assessment of falls will be done using the current gold standard of collecting monthly reports [45] returned by postal and/or electronic mail, an efficient (1-2 minute completion time) and effective method used by our team and others [41, 46-48]. In two prior studies we obtained 98% of monthly fall reports over 6 months [46, 49]. Participants will be provided with a monthly falls calendar to record falls when they occur, in order to reduce issues of recall and false negatives. Each participant that records a fall will be phoned to confirm that each fall meets the standard definition in order to reduce the risk of false positives, and to obtain information about the fall (e.g., how it occurred) and any resultant injury. An “injurious” fall is one that results in fractures, head injuries, sprains, bruises, scrapes, or serious joint injuries, or where the participant seeks medical care [13]. Of primary interest in the proposed study is the # of falls, with the # of injurious falls and medical care resulting from a fall being used for descriptive purposes of the study population.

Secondary Endpoint: Frailty will be measured using the components of the Frailty Phenotype [29]. The original 5 criteria of the phenotype (shrinking, exhaustion, low activity, slowness, and weakness) were limited to the measures available in the Cardiovascular Health Study [29]. The phenotype can now be measured more accurately with objective measures (e.g., lean body mass rather than self-report weight loss[50]). In this study, we will assess each frailty component using measures that will most accurately capture frailty criteria in the prostate cancer survivor population and where cutoff scores can be appropriately determined. A total frailty score will be calculated in the same manner as that of Fried:  $\geq 3$  criteria = frail; 1-2 criteria = prefrail; 0 criteria = robust. Since each variable is a continuous measure we will examine changes in each individual frailty component to determine how each intervention may shift frailty among our sample. Criteria are measured as follows:

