All analyses will retain each participant in the group he was randomly assigned regardless of missing data or drop out status (i.e., intention to treat). We will track medical treatment changes and disease progression during the study to describe the sample or justify why participants exited the study. In the unlikely event of a large subgroup, these data could be used for exploratory subgroup analysis to suggest directions for future research. Age, timing of ADT (current vs. past), fall history at enrollment and baseline frailty will be considered as possible covariates in all analyses. Age and timing of ADT (past vs current) are included since they may affect exercise tolerance and/or responsiveness to exercise training; fall history is included because we want to examine the efficacy of the interventions to reduce falls in men with a fall history and prevent falls

among men who have not recently fallen. Analyses will be conducted in Stata, R, and/or Mplus statistical software packages. Full information maximum likelihood estimation (FIMLE) will be used to estimate the models, as appropriate, because it is less biased and more efficient than other techniques for handling missing or incomplete data[92].

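### The injurious-falls analysis is confined to men who fell, so it estimates injury given a fall and not whether exercise reduces injurious falls

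*Combined protocol and SAP*

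**What the plan says.** Section 13.0, Additional Analyses, acknowledges that "the proposed study is not powered to examine reductions in injurious falls from the intervention" but plans an additional analysis because the outcome is important. The analysis set and model are: "We will conduct this analysis among the subsample that had at least 1 fall using logistic regression". No time window or model terms are given.

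Four other places bear on this:

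- Section 2.0 (primary aim hypothesis): "Tai ji quan and strength training groups will each reduce the incidence of falls compared to a control group".
- Section 13.0 (intention-to-treat statement after Power and Sample Size): "All analyses will retain each participant in the group he was randomly assigned regardless of missing data or drop out status".
- Section 13.0 (Aim 1): total falls per participant from baseline to 6 months are modelled by negative binomial regression, with no restriction to fallers.
- Section 3.0 (Primary Endpoint: Falls): falls are primary, "with the # of injurious falls and medical care resulting from a fall being used for descriptive purposes of the study population".

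No by-arm comparison of injurious falls in all randomised men is planned anywhere.

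**The concern.** The question is framed as an effect of the intervention on injurious falls. A man can avoid an injurious fall by not falling, or by falling without injury. Restricting to fallers discards the first route, which is the one the trial is built to test.

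It also selects on a post-randomisation variable that treatment is expected to change. The men who still fall on exercise need not resemble the men who fall on control, so randomisation no longer protects the comparison.

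The text does not say when the one fall must occur. Falls during the study is the natural reading, because the analysis concerns injuries from falls and section 13.0 uses a separate term for fall history at enrolment.

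This would be the trial's only modelled treatment comparison on injury. A reader could take its odds ratio as the effect on injurious falls when it may be diluted, null or reversed relative to that effect.

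**Working it through.** The plan states no power or event figure for this analysis, so there is none to reproduce. The check compares the fallers-only contrast with the all-randomised contrast.

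**Inputs from section 13.0.** A 47% reduction in fall rate (rate ratio 0.53), 100 evaluable men per group, alpha .05, Phi 2.5, R² .25, 80% power, and 20%-30% of older adults falling within 1 year.

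**Assumed inputs.** Control mean falls over 6 months (0.45, 0.75, 1.13). Injury risk per fall (30%, 50%). Phi read either as variance/mean or as negative binomial dispersion k.

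**Where the control means come from.** With the Poisson-regression sample-size formula the protocol cites, a two-sided test and exposed share 1/3, the control mean that makes N = 300 is

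2.5 × (1.96√4.5 + 0.842√7.16)² / (300 × 0.635² × 0.75) = 1.13.

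Other readings of that calculation (one-sided, R² = 0, exposed share 1/2) give 0.58 to 1.13. The low value, 0.45, gives 24-26% fallers, inside the protocol's 20%-30%, although that range is quoted for 1 year. The middle value, 0.75, lies between.

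**Step 1: the identity.** P(injured) = P(fall) × P(injured | fall). Suppose 30% of controls fall, exercise multiplies this by 0.53, and 30% of fallers are injured in both arms. Injured men per 100 are 30 × 0.30 = 9.0 against 15.9 × 0.30 = 4.8, a risk ratio of 0.53. The fallers-only odds ratio is 1.00, and would be for any reduction in falling.

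**Step 2: constant injury risk per fall.** For negative binomial falls with mean μ and dispersion k, P(at least one fall) = 1 − (1 + kμ)^(−1/k). Injurious falls at risk q per fall have mean qμ and the same k. With μ = 1.13, k = 1.33, q = 0.30:

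| | Control | Exercise | Odds ratio |
|---|---|---|---|
| Any injurious fall, all men | 24.4% | 14.9% | 0.54 |
| Injured, among fallers | 49.0% | 41.8% | 0.75 |

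Over all 12 settings (three means, two readings of Phi, two injury risks) the odds ratio is 0.54-0.59 in all men and 0.74-0.82 in fallers.

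**Step 3: reversal.** Let total falls drop 47% but injurious falls only 30%. In the same setting:

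| | Control | Exercise | Odds ratio |
|---|---|---|---|
| Any injurious fall, all men | 24.4% | 18.6% | 0.71 |
| Injured, among fallers | 49.0% | 52.3% | 1.14 |

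Over the 12 settings: 0.71-0.75 in all men, 1.13-1.59 in fallers. This scenario implies injury risk per fall rising by 0.70/0.53 = 1.32, that is from 30% to about 40% or from 50% to about 66%.

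**Step 4: simulation of the Step 2 settings.** 20,000 replicates, two arms of 100, unadjusted logistic Wald test, no attrition:

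| | Fallers only | All randomised |
|---|---|---|
| Power | 5-10% | 17-48% |
| Estimate above 1 | 25-38% | 2-11% |

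A negative binomial count of injurious falls in all men (control means 0.45 and 1.13) has power of 22-63% by normal approximation.

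**The case against.** The strongest reply is low consequence. The analysis is additional, declared unpowered, and carries no aim or hypothesis; section 3.0 gives injurious falls a descriptive role. The all-randomised version is also underpowered. This stands, and it limits the severity.

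Second, the wrong-direction rate counts point estimates whatever their precision. In the settings checked, a statistically significant wrong-direction result among fallers occurred in only about 1% of replicates or fewer. This also stands: the risk is a misleading estimate with a wide interval, not a false claim of significant harm.

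Third, reversal needs injury risk per fall to rise under exercise, which nothing in the documents suggests. With constant risk per fall the odds ratio stays below 1 in all 12 settings. That is right, so attenuation is the base case and reversal a possibility.

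Fourth, the intention-to-treat sentence mainly addresses dropout and missing data, and fallers do keep their assigned group. Fair; the firmer ground is selection on a post-randomisation outcome, although dropping every non-faller sits poorly with a statement covering all analyses.

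Fifth, injury given a fall is a legitimate question beside the Aim 1 result. It is, but the section poses a different one: reductions in injurious falls from the intervention. None of these replies repairs that mismatch.

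**Conclusion.** The concern holds. As written, the analysis targets injury given a fall in non-randomised subgroups, while the section asks about the effect on injurious falls. That conclusion needs no assumed figure.

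Its size does. Under a 47% fall reduction and constant injury risk per fall, much of the benefit disappears from the odds ratio. If exercise spares mainly non-injurious falls, the direction reverses. These figures rest on assumed fall rates and injury risks, and on a two-arm simulation without covariates or attrition.

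The plan should be changed, but nothing in the primary analysis depends on it. The gain is the correct target and far fewer wrong-direction estimates, not adequate power.

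**What to change.** Replace the fallers-only model with a by-arm comparison in all randomised men over a stated window, baseline to 6 months as in Aim 1. Either of these will serve:

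- number of injurious falls by negative binomial regression with a log(observed time) offset; or
- any injurious fall, yes or no, by logistic regression with non-fallers counted as no.

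Use the two Aim 1 treatment dummies and whatever covariate set is finally fixed for Aim 1; section 13.0 lists age, ADT timing, fall history and baseline frailty only as possible covariates. Label the result exploratory and report confidence intervals. Keep the proportion injured among fallers as description, named as injury given a fall.

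A separate editorial point, with no weight in the conclusion: use one definition of injurious fall. Section 3.0 has "fractures, head injuries, sprains, bruises, scrapes, or serious joint injuries, or where the participant seeks medical care"; Additional Analyses has "results in fractures, head injuries, sprains, or serious joint injuries, or in a participant seeking outside medical attention", without bruises and scrapes.

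The cost is wording only. Falls are already reported monthly by every participant, and injury is asked about at each fall confirmation call.
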